4.2.1 Primary Endpoint

The primary efficacy variable is serum potassium [S-K] level during the RTP, Days 8-29, using c-lab, or adjusted i-STAT for visits where c-lab is not available.

4.2.1.1 Definition

Several intercurrent events of concern have been identified in this setting, namely the use of disallowed medications, changes in treatment, including discontinuations, and death. For the main analysis of the primary endpoint a treatment policy approach to all the identified intercurrent events will be used (except for death, for which such an approach is not applicable).

However, a supplementary analysis aimed at evaluating the impact of disallowed medication use is included. In this analysis, the S-K (or i-STAT, if applicable) measurements obtained while a subject was receiving disallowed medication are excluded, reflecting a hypothetical scenario where disallowed medication is not available to subjects (i.e. a "hypothetical strategy" type of approach, see ICH E9 (R1) 2017 p. 18).

4.2.1.2 Derivations

See section 3.3.1.1 for definition of baseline for the efficacy analyses.

4.2.1.3 Handling of Dropouts and Missing Data

The S-K levels used for the primary analysis will be based on the c-lab measurements obtained during the RTP. Missing S-K c-lab values will be replaced as described in Section 3.3.5.

For the supplementary analysis aimed at evaluating the impact of usage of disallowed medications, if a subject is missing both the central laboratory and i-STAT values they will be imputed using multiple imputation (MI). Note that MI will not be used for the main analysis, as it is expected that, after i-STAT imputation, the amount of missing data will be minimal, and the missing pattern will be MAR, and would be sufficiently explained by the covariates included in the model.

Multiple imputation for the supplementary analysis

Multiple imputation (MI) will be done where imputation of unavailable c-lab values with i-STAT values not possible.

Missing S-K values will be imputed using the Fully Conditional Specification (FCS) method (Brand 1999; Van Buuren 2007). The covariates to be included in the imputation model are; the available c-lab data obtained post randomization visit (RTP Day 1) with baseline

covariates for the open-label initial phase eGFR, the open-label initial phase S-K values, the 28-day randomized treatment study phase S-K values as well as age (<55, 55-64, >64 years), baseline binary indicators for RAAS inhibitors, chronic kidney disease, heart failure, diabetes and treatment arm. The imputation will be performed using the log-transformed S-K values. M=100 will be chosen as the number of imputed data sets, the seed will be set as 22438 and the default 20 burn-ins will be used. An unstructured marginal covariance structure will be assumed. If the specified model fails to converge, alternative structures will be used as described in Section 3.3.6.

Analysis:

Once M complete data sets have been constructed using MI, the statistical analysis will be conducted on each of the M complete data sets. Explicitly, a linear mixed models will be applied, see Section 4.2.1.4.

Pooling:

Rubin's rules will be implemented for combining estimates and standard errors across the imputed data sets and conducting the analysis. Suppose \hat{Q}_i and \hat{W}_i are the point and variance estimates from the ith imputed data set, i = 1, 2, ..., 100. Then the combined point estimate for Q from multiple imputation is the average of the 100 complete-data estimates:

$$\bar{Q} = \frac{1}{100} \sum_{i=1}^{100} \hat{Q}_i$$

4.2.1.4 Main Analysis of Primary Endpoint

To address the primary objective, a comparison between placebo and each ZS treatment group (high to low) with regards to the mean S-K level during the 28-day randomized treatment study phase Days 8-29 will be made.

Descriptive statistics will be presented for S-K values at randomization visit (RTP Day 1) through Visit 14 (RTP Day 29), and the EOS visit. Mean change (absolute and percent change) from baseline will be summarized by treatment groups (ZS 5g, ZS 10g and placebo). In addition, a box plot of S-K values by visit will be presented.

The primary efficacy endpoint will be analyzed using a longitudinal mixed model (SAS PROC MIXED). The model will include all S-K data values (natural log scale) collected at the scheduled visits between Days 8-29 as response variables, and treatment, visit, treatment-by-visit interaction, baseline eGFR, OLP and RTP baseline S-K values as well as age (<55, 55-64, >64 years) and baseline binary indicators for RAAS inhibitors, chronic kidney disease, heart failure, and diabetes mellitus as fixed effects, patients are random effect term.

The p-value from least square mean (LSMEAN) (two-sided) will be provided to compare the overall mean difference in S-K values between each active treatment (ZS 10g and ZS 5g) and placebo (the second and third tests in the sequential closed testing procedure).

The estimated mean difference in log-transformed S-K values between each of the active treatment groups (ZS 10g and ZS 5 g) relative to the placebo treatment group will be provided along with accompanying 2-sided 95% confidence intervals. The relative difference in back-transformed S-K, ZS 10g and ZS 5 g vs placebo, will also be presented, along with the corresponding 2-sided 95% CI.

4.2.1.5 Supplementary and Sensitivity Analyses of Primary Endpoint

A sensitivity analysis will be conducted to assess the potential discrepancy in observed effect as assessed through by c-lab potassium, as opposed to i-STAT. This will be performed by using the same longitudinal model as was used for the main analysis of the primary endpoint on subjects Day 8 to Day 29 i-STAT measurements.

A supplementary analysis, aimed at evaluating the impact of the usage of disallowed medications on the efficacy results, will also be conducted. This will be done by means of removing the potassium measurements that occurred while a subject was receiving a disallowed medication (between medications start date and stop date, plus 7 days), replacing them using a MI approach, and replicating the main analysis on each of the resulting data sets. See Section 4.2.1.3 for details on the MI procedure.

4.2.1.6 Subgroup Analysis

The primary efficacy endpoint will be evaluated in several sub-groups, in order to explore the consistency of the treatment effect, as follows:

- chronic kidney disease status (yes/no)
- diabetes mellitus status (yes/no)
- heart failure status (yes/no)
- those on RAAS inhibitors (yes/no).

For the subgroup analysis to be conducted, a minimum of 10 subjects per treatment-subgroup combination is required, since this is the generally accepted minimum number. A single model will be fitted, this model including a treatment by subgroup interaction term in addition to the covariates in the original analysis (See section 4.2.1). Estimates of the treatment effect for each subgroup will be provided, with corresponding confidence intervals. A p-value for the interaction term will also be given. Additionally, LSMEAN for the combinations of treatment by subgroup levels will be presented with corresponding confidence intervals.

4.2.2 Secondary Endpoints for OLP phase

4.2.2.1 Definition

The secondary efficacy endpoints for OLP phase will include the following:

- 1. Proportion of subjects who achieve normokalemia during the OLP at 24 hours (OLP Day 2) and at the end of the OLP. Each subject is classified into a responder or a non-responder category (i.e. a 0-1 type of response for subjects who achieve normokalemia or subjects who do not achieve normokalemia), with a subject being a responder if they have S-K between 3.5 and 5.0 mmol/L, inclusive. The following 7 time points during the OLP phase will be considered:
 - OLP Day 1, at 1, 2 and 4 hours post first dose
 - OLP Day 2, pre-dose and 1 hour post dose
 - o OLP Day 3, pre-dose
 - End of OLP

Note: not all subjects will have OLP Day 2, 1 hour post dose and OLP Day 3 pre-dose visit.

2. Exponential rate of change in S-K levels (blood) at 24 hours during OLP

- 3. Mean change (absolute and percent (%) change) from baseline in S-K levels at all measured time intervals post-dose during OLP listed above.
- 4. Time to normalization in S-K levels (normalization defined as first time S-K levels between 3.5-5.0 mmol/L, inclusive, are achieved) during OLP

4.2.2.2 Derivations

See section 3.3.1.1 for definition of baseline for the efficacy endpoints.

Time to normalization is defined as the number of hours from the first administration of IP in OLP to the date-time of normalization = (date-time of normalization – date-time of first IP administration). For analysis of time to normalization, subjects who fail to achieve normalization will be censored at the time of last SK measurement in the OLP.

For analysis of the exponential rate of change, time (in hours) from first dose of IP will be derived as (datetime of SK measurement – datetime of first dose of IP)/3600.

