- The proportion of patients who remain normokalemic (as defined by S-K between 3.5-5.0 mmol/L, inclusive) at the end of the 28-day randomized treatment study phase and during the 28-day randomized treatment study phase.
- The number of days patients remain normokalemic during the 28-day randomized treatment study phase.
- The mean change and mean percent change in S-K levels evaluated relative to both baselines.
- The time to hyperkalemia (defined as $S-K \ge 5.1 \text{ mmol/L}$).
- The mean change in S-Aldo and P-Renin levels.

Safety endpoints will include adverse events (AEs), serious AEs (SAEs), vital signs, clinical laboratory evaluations, physical examinations, ECGs, and other serum electrolytes (specifically, serum calcium [S-Ca], serum magnesium [S-Mg], serum sodium [S-Na], serum phosphate [S-PO₄], serum bicarbonate [S-HCO₃], and blood urea nitrogen [BUN]).

The confirmed i-STAT potassium value on Study Day 2 or Day 3 of the open-label initial phase will be used to established the patient's eligibility into the 28-day randomized treatment study phase, however central laboratory S-K values will be used for all analyses.

Sensitivity analyses will be conducted to assess the robustness of the results of the primary analysis and the secondary analysis of the proportion of normokalemic patients at the end of the 28-day randomized treatment study phase and during the 28-day randomized treatment study phase.

There is no planned interim analysis in this study.

Assuming an inter-subject standard deviation of 0.50, approximately 250 patients, (100 patients per active dose treatment arm and 50 patients for placebo control arm), will provide >90% power to detect a mean difference of 0.30 in mean 28-day randomized treatment phase Day 8-29, comparing each active dose (high to low) vs. placebo control using a two-sided t-test at a significance level of 5%. Assuming 90% of patients will be normokalemic after treatment in the open label initial phase (see Section 7.2), approximately 280 patients will be needed to enter the open-label initial phase.

TABLE OF CONTENTS

VERSIC	ON HISTORY	2
CLINIC	AL STUDY PROTOCOL SYNOPSIS	15
TABLE	OF CONTENTS	22
LIST OI	F ABBREVIATIONS AND DEFINITION OF TERMS	27
1.	INTRODUCTION	29
1.1	Background and rationale for conducting this study	29
1.2	Rationale for study design, doses and control groups	
1.3 1.3.1 1.3.2 1.3.3	Benefit/risk and ethical assessment Clinical benefits Clinical risks Clinical benefit-risk balance	34 34

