4.3.2 Open-label initial phase Day 2 (Visit 4)

Patients will arrive fasting at the clinic in the morning (nothing by mouth except water for a minimum of 8 hours prior to potassium sample collection at the clinic). They will bring the used and/or unused IP and completed dosing schedule card with them.

- The clinic staff will solicit any AEs, note any changes in concomitant medications, examine the IP and make note of the time the doses were taken and any unused IP on the eCRF and source documents.
- Potassium levels will be evaluated by i-STAT and the Central Laboratory. i-STAT potassium measurement will be done during the visit to determine the next steps of procedures.
 - If the i-STAT potassium value is < 3.5mmol/L, see Section 7.2 regarding how to handle patients.
 - If the i-STAT potassium value is between 3.5 and 5.0 mmol/L inclusive the patient will skip the remaining procedures for initial phase Day 2 and will be randomized (on the same day) into the 28-day randomized treatment study phase, and complete the remaining procedures detailed in Section 4.3.4. In this case Visit 4 will be skipped completely and the patient will conduct the Randomization visit instead. No data entry is done in the Visit 4 eCRF.

- If the i-STAT potassium value is \geq 5.1 mmol/L, the patient will receive an additional 24 hours of ZS 10g TID and the following procedures will be performed.
- An ECG will be performed (Section 5.2.3)
- Following completion of the above procedures, the first daily dose of IP will be administered in the clinic as a slurry/suspension in water, followed by the 1 hour post Dose 1 blood draw (see Figure 4 for the flow chart based on the potassium value), after which the patient is allowed to break the fast.
- Patients will then be sent home with study drug and instructions on how to take the IP. They will be requested to fill out a dosing schedule card indicating when they took the IP.
- Patients will return to the clinic the following morning and bring the used and/or unused IP and completed dosing schedule card with them.

4.3.3 Randomization Visit - For patients not entering the 28-day randomized treatment study phase

On Day 3 of the Open-Label initial phase, patients will arrive at the clinic in the morning, fasting (nothing by mouth except water for a minimum of 8 hours prior to potassium sample collection at the clinic). They will bring the used and/or unused IP and completed dosing schedule card with them.

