3.3.2.2 Secondary hypotheses

For the OLP, the following hypotheses will be tested versus two-sided alternatives:

Endpoint: Exponential rate of change in S-K levels (blood) at 24 hours and 48 hours during OLP.

The null hypothesis:

$$H_0$$
: Exponential rate A_{S-K} (24 hours) = 0 vs. H_A : Exponential rate A_{S-K} (24 hours) $\neq 0$

 H_0 : Exponential rate $\Delta S-K$ (48 hours) = 0 vs. H_A : Exponential rate $\Delta S-K$ (48 hours) $\neq 0$

This is evaluated by the parameter estimate of time (in hours) from a mixed effects model as described in Section 4.2.2.4. Note that the exponential rate of change refers to the degree of decline in SK values over time, which is assumed to follow an exponential trend.

Endpoint: Mean change (absolute and percent (%) change) from baseline in S-K levels

The null hypotheses:

$$H_0: \mu_{\Delta S-K} (24 \text{ hours}) = 0 \text{ vs. } H_A: \mu_{\Delta S-K} (24 \text{ hours}) \neq 0$$
$$H_0: \mu_{\Delta S-K} (End \text{ of } OLP) = 0 \text{ vs. } H_A: \mu_{\Delta S-K} (End \text{ of } OLP) \neq 0$$

The end of OLP can be 24 or 48 hours depending on the duration of OLP, as subjects who did not achieve normokalemia at 24 hours are evaluated again at 48 hours.

There will be a similar hypothesis for the mean percent change of S-K at 24 and 48 hours.

For the RTP, the following hypotheses will be tested:

Endpoint: Proportion of subjects who remain normokalemic at the end of the RTP and during the RTP.

The null hypotheses:

$$H_0: OR \left(ZS_{10g} vs Placebo \right) = 1. vs. H_A: OR \left(ZS_{10g} vs Placebo \right) \neq 1$$
$$H_0: OR \left(ZS_{5g} vs Placebo \right) = 1. vs. H_A: OR \left(ZS_{5g} vs Placebo \right) \neq 1$$

For each of the treatment arm comparisons, two tests will be done: one aiming at evaluating the odds of being normokalemic Day 8-29, performed by means of a generalized random effects model as described in Section 4.2.3, and another aiming at evaluating the probability of being normokalemic at Day 29 in particular, performed by means of a logistic regression model.

Endpoint: Number of days subjects remain normokalemic during the RTP.

The null hypotheses:

 $H_0: \mu_{\text{days of normokalemic}}(ZS_{10g}) = \mu_{\text{days of normokalemic}}(Placebo) \text{ vs.}$ $H_A: \mu_{\text{days of normokalemic}}(ZS_{10g}) \neq \mu_{\text{days of normokalemic}}(Placebo)$

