3.3.5 Handling of Missing Serum Potassium (S-K) Data

The S-K levels used for all analyses will be based on the central laboratory (c-lab) measurements. If the S-K c-lab data points are missing, the i-STAT data will be used to replace missing data by adjusting for the average paired difference between the c-lab and i-STAT levels collected at the same visit and with the same calibration method for the potassium assay. If the time difference between the SK c-lab and i-STAT measurements is greater than 15 minutes, the SK measure for that time point will be set as missing.

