4.2.2.4 Primary Analysis of Secondary Endpoints (OLP)

Descriptive statistics will be presented for S-K levels at baseline, OLP Day 1 (1, 2 and 4 hours post first dose) and OLP Day 2 (pre-dose and 1 hour post the first dose in the day), OLP Day 3 (pre-dose) and end of OLP, including the mean change (absolute and percent change) from baseline. In addition, a box plot of S-K values by timepoint will be presented.

Similarly, descriptive statistics tabulating the proportion of subjects who achieve normokalemia at each of the timepoints specified above will be presented.

Proportion of subjects who achieve normokalemia

The observed proportions of subjects achieving normokalemia at 24 hours (OLP Day 2) and end of OLP will be provided along with 95% two-sided Clopper-Pearson exact confidence intervals.

Exponential rate of change

The exponential rate of change in S-K levels will be derived from a longitudinal mixed model (SAS PROC MIXED, see Section 3.3.5) of log-transformed S-K levels during the OLP. Measurements up to and including 24 hours post-dose will be used as the response variable. The model will include OLP baseline eGFR, OLP baseline S-K values as well as age (<55, 55-64, >64 years), time (in hours) and baseline binary indicators for RAAS inhibitors, chronic kidney disease, heart failure, and diabetes mellitus as fixed effects terms. A random intercept and slope (for time) will be used in the model. The exponential rate of change will correspond

to the estimate of the parameter describing the SK decline over time, i.e. the slope in terms of log SK. It will be presented with corresponding standard error, 95% confidence interval and p-value.

Mean change (absolute and percent change) from baseline

For changes and percent changes from baseline in S-K levels at 24 hours (OLP Day 2) (and end of OLP, one sample, two-sided t-tests will be applied to test the null hypotheses that the means are equal zero. The estimates, corresponding SD, 95% 2-sided CI and p-values will be presented.

Time to normalization in S-K values

The time to normalization in S-K levels will be summarized using Kaplan-Meier life table curves and associated 95% CI points will be provided at 1, 2, 4, 24 and 48 hours post first dose of IP.. All S-K assessments during OLP will be used.

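### Time to normalization in the open-label phase: subjects who leave without normalising are censored, so the 48-hour Kaplan-Meier value can exceed the share who normalised by then, and the target is not stated

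*SAP*

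**What the plan says.** - **Event.** SAP 4.2.2.1 has "normalization defined as first time S-K levels between 3.5-5.0 mmol/L, inclusive, are achieved", during the OLP.
- **Assay for the event.** SAP 3.3.5 states: "The S-K levels used for all analyses will be based on the central laboratory (c-lab) measurements". Adjusted i-STAT is used only where the central value is missing. The protocol synopsis says the same: "however central laboratory S-K values will be used for all analyses".
- **Assay for leaving the phase.** Protocol 4.3.2 states: "If the i-STAT potassium value is between 3.5 and 5.0 mmol/L inclusive the patient will skip the remaining procedures", and such a patient is randomised that day. Protocol 4.3.1 also takes a patient out on Day 1 if i-STAT is above 6.2 mmol/L 90 minutes after the second dose. SAP 3.3.2.2 accepts the variable length: "The end of OLP can be 24 or 48 hours depending on the duration of OLP".
- **Censoring.** SAP 4.2.2.2: "subjects who fail to achieve normalization will be censored at the time of last SK measurement in the OLP". Time is the difference between two actual date-times.
- **Estimator.** SAP 4.2.2.4 uses Kaplan-Meier, and "associated 95% CI points will be provided at 1, 2, 4, 24 and 48 hours post first dose of IP".
- **Estimand.** The table in SAP 4.2 assigns a treatment policy strategy to all four open-label endpoints. No competing-event rule is given.

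**The concern.** Most patients randomised at 24 hours should already be events, because their central potassium was in range then or earlier. Two groups are not: those in range on i-STAT whose central value never was, and those stopped on Day 1 before any central value was in range. Neither can normalise during the OLP any more.

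Censoring tells Kaplan-Meier that they are still at risk and will go on to normalise at the rate of those who remain. Those who remain after 24 hours are selected on potassium: they stayed because i-STAT was still high, or was low and under the handling in protocol 7.2. Exit is therefore related to the outcome, and censoring for it is informative. It also sits badly with a treatment policy strategy, since it replaces what happened with what might have happened under continued open-label dosing.

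At stake is a protocol secondary endpoint in a single-arm phase, where no control arm shares the error. The clinical study report would carry a 48-hour Kaplan-Meier value beside an end-of-OLP proportion, with no stated reason for a difference between them.

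**Working it through.** **Inputs**
- Illustrative rates: 77% normokalemic within 24 h and 86% within 48 h (protocol 1.3.1, prior study).
- About 280 patients entering the OLP (protocol 8.2).
- Assumed, not in the documents: 55% normalised by 4 h; a share c censored at 24 h; a share d stopped on Day 1 without normalising.

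**The plan's own figure.** The documents give no Kaplan-Meier value for this trial. The nearest open-label figure is the entry number: 250/0.90 = 277.8, so 278, against about 280 stated. It reproduces.

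**Excess over the observed share.** With F4 = 0.55, F24 = 0.77 and F48 = 0.86 as the shares actually normalised:

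S(48) = (1−F4) × [1 − (F24−F4)/(1−F4−d)] × [1 − (F48−F24)/(1−F24−d−c)]

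With d = 0 the 4-hour assumption cancels, S(48) = 0.23 × [1 − 0.09/(0.23−c)], and the excess is 0.09c/(0.23−c).

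| c | Kaplan-Meier at 48 h | Excess over 86% |
|---|---|---|
| 0 | 86.0% | 0 |
| 0.3% | 86.1% | 0.12 points |
| 1% | 86.4% | 0.41 points |
| 2% | 86.9% | 0.86 points |
| 3% | 87.35% | 1.35 points |
| 5% | 88.5% | 2.5 points |

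The standard error of an 86% proportion is √(0.86×0.14/280) = 2.07 points. Half of that, 1.04 points, needs c of about 2.4%. With c = 3% and d = 1%: 1 − 0.45 × (1 − 0.22/0.44) × (1 − 0.09/0.19) = 88.2%, an excess of 2.2 points.

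Another parametrisation holds the later rate among those who stay at 9/23 = 39.1%. Kaplan-Meier then remains at 86.0% while the observed share is 77 + (23−c)×9/23 (c in points), so the excess is c×9/23: 0.8, 2.0 and 3.9 points for 2, 5 and 10% censored.

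**Against everyone treated for 48 hours.** Fix that target at 86% and censor 5% at 24 h. If the censored patients would have normalised at rate r by 48 h, those who stay have rate (9−5r)/18, and Kaplan-Meier gives 77 + 23 × that rate.

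| r | Kaplan-Meier | Observed | Target |
|---|---|---|---|
| 20% | 87.2% | 85.0% | 86.0% |
| 39% | 86.0% | 84.0% | 86.0% |
| 60% | 84.7% | 83.0% | 86.0% |
| 80% | 83.4% | 82.0% | 86.0% |

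The direction depends on r. Patients already in range on i-STAT are plausibly the easier ones, so Kaplan-Meier more likely lies between the observed share and this target.

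**Actual clock times.** A simulation (2,800 patients per run, later rate 9/23, Day 2 and Day 3 samples spread evenly within ±1 h) gave:

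| Censored at 24 h | Kaplan-Meier at 48.0 h | Observed by 48.0 h | Observed, end of OLP | Kaplan-Meier after last visit |
|---|---|---|---|---|
| 0 | 82.6% | 81.7% | 86.1% | 99.0% |
| 5% | 83.7% | 80.6% | 84.1% | 98.8% |

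The last column arises because Day 3 failures sampled early leave the risk set before later Day 3 successes. If sampling order is unrelated to outcome, the expected final value is 1 − 0.23 × ∏(1 − h/r), r = 1 to m, with h = 9/23 and m patients on Day 3. For 280 patients and nobody censored at 24 h, m = 0.23×280 ≈ 64; the product is 0.133 and the curve ends near 97%, against 86% observed.

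**The case against.** **No inference rests on it.** Time to normalization is absent from SAP Table 3 and has no hypothesis in SAP 3.3.2.2. This stands and limits the priority.

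**The observed proportions are reported anyway.** SAP 4.2.2.4 gives them at 24 hours and end of OLP with exact intervals, and descriptively at each time point. That is a useful check with no censoring. But they record status at each time, not first normalization by that time, so they do not replace a valid time-to-event curve.

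**Few patients may be affected.** Censoring at 24 hours needs a central value out of range at 1, 2, 4 and 24 hours with i-STAT in range. Protocol 1.3.1 gives a median time to normokalemia of 2.2 hours in the prior study. This stands: the number may be small, and early exits have little bearing on the 1-, 2- and 4-hour estimates.

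**Nominal times may already apply.** The footnotes to SAP Table 2 label the Day 2 and Day 3 pre-dose samples as the 24- and 48-hour measurements for all analyses. The specific derivation in SAP 4.2.2.2 nevertheless subtracts date-times. At best the SAP is ambiguous.

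**Stronger readings that the documents do not support.** A reader might infer that the 48-hour value overstates normalization without qualification. It does so only against the share normalised by the same time; against everyone treated for 48 hours it may be too low. A reader might infer that it must exceed the end-of-OLP proportion. With samples scattered around 48 hours it need not (83.7% against 84.1% above). A reader might infer a material bias under any plausible assay agreement. No agreement data are given, and at 0.3% censored at 24 hours the excess from that source is only 0.12 points.

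**Conclusion.** The concern holds in a limited form. Censoring at OLP exit is informative, and the Kaplan-Meier value at 48 hours is at or above the share who had actually normalised by then. It is not in general the all-treated-for-48-hours share either. The size cannot be fixed from the documents: about 0.1 to 2.5 points for 0.3 to 5% censored at 24 hours, and zero from this source if no one is. These figures rest on prior-study rates and, where Day 1 stops are included, on an assumed 55% normalised by 4 hours. The clock-time artefact is separate. It needs no one censored at 24 hours, only Day 3 samples at scattered times, and it makes the plotted curve after 48 hours unreliable. Priority is low to moderate.

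**What to change.** In SAP 4.2.2.2 and 4.2.2.4:

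1. State that the target is normalization during the OLP as conducted.
2. Treat leaving the OLP without a central potassium of 3.5–5.0 mmol/L (randomised on i-STAT, open-label treatment stopped, or phase completed without normalising) as a competing event. Report the Aalen-Johansen cumulative incidence at 1, 2, 4, 24 and 48 hours with 95% CI (PROC LIFETEST with the EVENTCODE option). If no data are lost, this equals carrying these subjects as not normalised through 48 hours.
3. Use nominal times for the 24- and 48-hour pre-dose samples, in line with the footnotes to SAP Table 2.
4. Keep censoring only for potassium data lost while a subject is still in the OLP.

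The cost is SAP wording and one procedure option, with no new data. The 48-hour figure may be slightly less favourable. It will not estimate the result had everyone continued for 48 hours; if that is wanted, it needs its own estimand and assumptions.
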